#### 9.4.2 Enrolment characteristics

- Body Surface Area (m^2, 2 decimal figures)
- Predniso(lo)ne induction regimen (1A/1B)
- ANCA type (anti-PR3/anti-MPO)
- Relapse type (Severe/Non severe)
- Induction dose of Rituximab (mg/infusion)

#### 9.4.3 Stratification variables

---

 Calculated using the Du Bois formula (14)

The Enrolment Form records the stratification variables at baseline (Month 0): prednisolone induction regimen, ANCA type, and relapse severity. The following frequency tables will be summarised in accordance with section 9:

- Relapse severity (Severe/Non-severe) stratified by prednisolone regimen (1A/1B).
- ANCA type (anti-PR3/anti-MPO) stratified by prednisolone regimen (1A/1B).
- Relapse severity (Severe/Non-severe) stratified by ANCA type (anti-PR3/anti-MPO).

Corresponding mosaic plots will also be produced.

## 9.5 Concurrent Illnesses and Medical Conditions

Any relevant medical history, as specified in the Baseline Medical History Form, will be recorded at the screening visit and entered in the MACRO database.

The following baseline medical history variables will be summarised in accordance with section 9 using the full analysis population. Frequency tables will be presented by treatment allocation (“Azathioprine”, “Rituximab”) and further sub-divided by induction regimen at enrolment (“1A”, “1B”).

### 9.5.1 Baseline Medical History

- Prior disease duration (years) – derived variable, details in section 9.2
- Historical ANCA positivity – derived variable, details in section 9.2
- Historical organ involvement, broken down by Body System and abnormality type, (counts):
  - Constitutional Symptoms
  - Joints
  - Skin
  - Mucous membranes/Eyes
  - Ear/Nose/Throat
  - Heart
  - Gastrointestinal tract
  - Lungs
  - Kidneys
  - Nervous system
  - Other

- Total number of Body Systems affected – derived variable, details in section 9.2
- Co-morbidities (counts):
  - Hypertension
  - Ischemic Heart Disease (IHD)
  - Chronic Lung Disease (COPD)
  - Cerebrovascular Disease (CVD)
  - Cancer
  - Venous Thromboembolism
  - Diabetes Mellitus

## 9.6 Prior and Concurrent Medications

Previous medication history to treat vasculitis as specified in the Baseline Medical History Form (Medication History section) will be recorded at the screening visit and entered in the MACRO database.

The following baseline medical history variables will be summarised in accordance with section 9 using the full analysis population. Frequency tables will be presented by treatment allocation (“Azathioprine”, “Rituximab”) and further sub-divided by induction regimen at enrolment (“1A”, “1B”).

### 9.6.1 Prior treatment

Number of patients who have ever received the following as a treatment for vasculitis:

- Methylprednisolone
- Prediso(lo)ne
- Oral Cyclophosphamide
- IV Cyclophosphamide
- Cyclophosphamide (CYC) – derived variable, details in section 9.2
- Rituximab
- Azathioprine
- Methotrexate
- Mycophenolate Mofetil
- Sulfamethoxazole/Trimethoprim
- Plasma Exchange

- IVIG
- Anti-TNFs
- Other immunosuppression

Doses for the following treatments:

- Rituximab (mg)
- Oral Cyclophosphamide (g)
- IV Cyclophosphamide (g)
- Cumulative cyclophosphamide dose (g) – derived variable, details in section 9.2

Total counts of the following treatments:

- Number of prior immunosuppressants (excluding glucocorticoids) – derived variable, details in section 9.2

### 9.6.2 Concomitant Medication

Any relevant concomitant medication prescribed during the trial will be recorded in the Concomitant Medication Form at Screening, months 0 to 48 and Unscheduled visit if applicable. The data will be entered in the MACRO database and retained for safety monitoring. Data will be reported as table listings per patient, per study visit. The following information, when available, will be reported:

- Medication name (generic names only)
- Category (Anticoagulant/Antiplatelet, IVIg, Antimicrobial, Other)
- Dose (units)
- Frequency (one daily, twice daily, three times daily, four times a day, alternate days, weekly, other, as required)
- Comments

## 9.7 Disease activity assessment (BVAS/WG)

The Birmingham Vasculitis Activity Score for Wegener's Granulomatosis (BVAS/WG) will be used to record disease activity (1).

---

 Concomitant medication from Screening to Month 4 visit were recorded in the Induction Phase analysis and report.

The BVAS/WG Form, automatically scored by MACRO, will be reported at Month 4, 8, 12, 16, 20, 24, 27, 30, 36, 42 and 48, using the full analysis population. The following variables will be summarised in accordance with section 9.

- The total count of Body Organ System involvement:
  1. General
  2. Cutaneous
  3. Mucous membranes/eyes
  4. Ear, nose & throat (ENT)
  5. Cardiovascular
  6. Gastrointestinal
  7. Pulmonary
  8. Renal
  9. Nervous system
  10. Other (all item's descriptions will be listed, by subject ID and visit)
- Total number of items:
  1. Major New/Worse
  2. Minor New/Worse
  3. Major persistent
  4. Minor persistent
- Total major items – calculated by MACRO
- Total minor items – calculated by MACRO
- Total BVAS/WG score – calculated by MACRO
- Current disease status – derived variable, details in section 9.2:
  1. Severe flare/new disease
  2. Limited flare/new disease
  3. Persistent disease
  4. Remission
- Physician's global assessment (PGA)

## 9.8 Disease related assessment (CDA)

The Combined Damage Assessment (CDA) Index will be used to record organ damage that has occurred in patients since the onset of vasculitis. Accrual of

---

 <https://onlinelibrary.wiley.com/doi/epdf/10.1002/1529-0131%28200104%2944%3A4%3C912%3A%3AAID-ANR148%3E3.0.CO%3B2-5>

0131%28200104%2944%3A4%3C912%3A%3AAID-ANR148%3E3.0.CO%3B2-5

damage as measured by the CDA score. Each persistent or new occurrence of damage is recorded as “Yes” and given a score of 1. The cumulative accrual of damage is obtained by summing across the different types of damage to get an overall score. CDA should never decrease, and items that are recorded at one visit should always be recorded at subsequent visits.

The CDA Form will be scored by cumulative sum of each of the Body Organ Systems detailed below, assigning a value of 1 for each item ticked as present (“Yes” checkbox ticked). Only the listed items contribute to the specified Body Organ System, non-listed items will be ignored. The “No” checkboxes will also be ignored: items are assumed to be not present unless the “Yes” checkbox has been explicitly ticked.

The CDA Form will be reported at Month 4, 12, 24, 36, 42 and 48 visits, using the full analysis population. The following CDA variables will be summarised in accordance with section 9.

- Damage to each Body Organ System, reported as a categorical variable (yes/no) surmising whether any listed sub-item is reported (i.e. “No” means a score of zero):
  - a. **Musculoskeletal**, max score = 5
    - 1 – Significant muscle atrophy or weakness (any item)
    - 2 – Deforming/erosive arthritis
    - 3 – Osteoporosis/vertebral collapse
    - 4 – Avascular necrosis
    - 5 – Osteomyelitis
  - b. **Skin/Membranes**, max score = 3
    - 1 – Alopecia
    - 2 – Cutaneous ulcers
    - 3 – Mouth ulcers
  - c. **Ocular**, max score = 7
    - 1 – Cataract
    - 2 – Retinal changes or Retinal artery occlusion or Retinal vein occlusion
    - 3 – Optical nerve atrophy
    - 4 – Low vision or Diplopia
    - 5 – Blindness in one eye (left or right)
    - 6 – Blindness in second eye (both)
    - 7 – Orbital wall destruction

- d. **ENT**, max score = 6
  - 1 – Sensorineural hearing loss or Conductive hearing loss (Ear section)
  - 2 – Chronic rhinitis/crusting (Nose section)
  - 3 – Nasal bridge collapse/saddle nose or Nasal septal perforation (Nose section)
  - 4 – Chronic sinusitis (Sinuses section)
  - 5 – Subglottic stenosis (no surgery) (Subglottic stenosis section)
  - 6 – Subglottic stenosis (surgery) (Subglottic stenosis section)
- e. **Pulmonary**, max score = 7
  - 1 – Pulmonary hypertension
  - 2 – Pulmonary fibrosis
  - 3 – Pulmonary infarction
  - 4 – Pleural fibrosis
  - 5 – Chronic asthma
  - 6 – Chronic breathlessness
  - 7 – Irreversible loss of lung function
- f. **Cardiac**, max score = 7
  - 1 – Angina or Percutaneous coronary intervention
  - 2 – Myocardial infarction
  - 3 – Coronary artery bypass graft
  - 4 – Cardiomyopathy (NYHA Class I/II or NYHA class III/IV)
  - 5 – Valvular Disease
  - 6 – Pericarditis or Pericardectomy
  - 7 – Hypertension (any item)
- g. **Vascular Disease**, max score = 8
  - 1 – Absent pulses in 1 limb
  - 2 – 2nd episode of absent pulses in 1 limb
  - 3 – Major vessel stenosis
  - 4 – Claudication > 3 months
  - 5 – Minor tissue loss
  - 6 – Major tissue loss
  - 7 – Subsequent major tissue loss
  - 8 – Deep venous thrombosis or Complicated venous thrombosis
- h. **Gastrointestinal**, max score = 4
  - 1 – Gut infarction/resection
  - 2 – Mesenteric insufficiency/pancreatitis
  - 3 – Esophageal stricture/surgery
  - 4 – Chronic peritonitis
- i. **Renal**, max score = 3
  - 1 – Estimated/measured GFR<50%

- 2 – Proteinuria (any item)
- 3 – End-stage renal disease or Dialysis
- j. **Neuropsychiatric**, max score = 8
  - 1 – Cognitive impairment (Psychiatric section)
  - 2 – Major psychosis (Psychiatric section)
  - 3 – Seizures (Neurological section)
  - 4 – Cerebrovascular accident (Neurological section)
  - 5 – 2nd cerebrovascular accident (Neurological section)
  - 6 – Cranial nerve lesion (Neurological section)
  - 7 – Sensory polyneuropathy (any item) or Motor Neuropathy (Neurological section)
  - 8 – Transverse myelitis (Neurological section)
- k. **Other**, max score = 6
  - 1 – Gonadal failure (Premature ovarian failure or Azoospermia)
  - 2 – Marrow failure (Refractory cytopenia or Myelodysplastic syndrome)
  - 3 – Diabetes mellitus
  - 4 – Chemical cystitis (any item) (Other section)
  - 5 – Malignancy (Bladder cancer or Cervical cancer or Hemotopoetic malignancy or Solid tumour malignancy)
  - 6 – Other (Other section)
- **Total CDA score, max = 64** – derived variable, details in section 9.2. The variable will be reported both as continuous and categorical, coarsening into ranges:
  - less than 5
  - 5–10
  - 11–15
  - 16–20
  - greater than 20
- **Change in total CDA score between month 4 and month 12** – derived variable, details in section 9.2
- **Change in total CDA score between month 4 and month 24** – derived variable, details in section 9.2
- **Change in total CDA score between month 4 and month 36** – derived variable, details in section 9.2

---

 A different scoring system from the one used for the Induction Phase report is employed here to calculate an overall CDA score. The new scoring system is based on COMBIVAS VDI (Vasculitis Damage Index) form. A comparison between the old and new system for the Induction Phase will be presented.

- **Change in total CDA score between month 4 and month 48** – derived variable, details in section 9.2
- **Change in total CDA score between month 24 and month 36** – derived variable, details in section 9.2
- **Change in total CDA score between month 24 and month 48** – derived variable, details in section 9.2

## 9.9 Treatment Compliance

Compliance to treatment during the maintenance phase of the trial was assessed based on information collected in the Treatment and Follow Up forms. A comprehensive overview of the process involved is described in a separate document. All randomised patients (full analysis population) were assessed by an independent committee for compliance to allocated treatment during the active maintenance phase (from randomisation to month 24) and during follow-up (from month 24 to end of trial). Outcomes were recorded into a spreadsheet sent to data management to be added to the main MACRO data download.

The following variables found in the spreadsheet will be summarised in accordance with section 9:

- Maintenance compliance (Yes/No) & reasons for non-compliance
- Follow-up compliance (Yes/No) & reasons for non-compliance

## 9.10 Treatment Exposure

In the maintenance phase, all patients allocated to rituximab treatment received rituximab 1000 mg x 1 dose at months 4, 8, 12, 16 and 20 and glucocorticoids. Patients randomised to the control arm will receive oral azathioprine, to be taken daily, with a target dose of 2mg/kg. The maximum daily dose allowed is 200mg. The maximum treatment period is 27 months, with tapering after month 24. In the event of azathioprine intolerance (see section 11.2.i of the protocol), methotrexate 25 mg/week will be substituted for patients with GRF > 50 ml/min, and mycophenolate Mofetil will be substituted for patients with GRF < 50 ml/min.

### 9.10.1 Rituximab treatment

---

 See *Medication Compliance.docx*

 See section 11.2 of the protocol for further details of azathioprine administration.

The Treatment form records details of rituximab treatment, at months 4, 8, 12, 16 and 20, as recorded by the PI. The form will be reported at each time point using the full analysis population. The following variables will be summarised in accordance with section 9:

- Rituximab dose (mg)
- Rituximab administered according to protocol (Yes/No)
- Reasons for non-compliance, counts:
  - a) Rituximab not administered as IgG < 3g/L
  - b) Incomplete
  - c) Interrupted
  - d) Other

Reasons given for incomplete/interrupted/other treatment non-compliance will be listed per patient, per visit.

In addition, total cumulative rituximab dose after 24 months as recorded in the Follow Up form as well as the following derived variable (details in section 9.2) will be calculated across the maintenance therapy period and summarised in accordance with section 9:

- Cumulative rituximab dose (mg) up to 24 months
- Total rituximab dose in maintenance phase (mg) – derived variable, details in section 9.2
- Overall full rituximab treatment (Yes/No) – derived variable, details in section 9.2
- Number of full rituximab infusions – derived variable, details in section 9.2

### 9.10.2 Glucocorticoid treatment

Concomitant glucocorticoid (GC) treatment in the maintenance phase was permitted as follows. A GC dose of 10 mg/day or less is a requirement for randomisation. GC reduces to 5 mg/day by month 6, according to schedule 2 (Table 7), and continues at 5 mg daily until month 16. GC dose is then reduced to 2.5mg/day and completely withdrawn at month 20.

---

 From randomisation to month 24 from enrolment inclusive.

 As recorded in the Follow Up form at month 24, it includes induction phase doses.

Table 7: CG Schedule 2

	Maintenance Schedule Daily Prednisolone dose (mg)
Week	
12	10
14	10
16 (randomisation)	10
18	7.5
20	7.5
22	5
24	5

Alternate day dosing regimens (i.e. those that use two different doses on alternate days) may be used to achieve the appropriate average daily dose required by the protocol but differences in alternative day doses may not be greater than 5 mg. For example, a dose of 7.5 mg/day may be achieved by alternating daily doses of 10 mg/day and 5 mg/day.

For all patients follow-up daily dose of prednisolone was recorded at each visit in the maintenance phase (months 4, 8, 12, 16, 20, 24, 27, 30, 36, 42 and 48) in the Follow-Up Form. Section 1 and 2 of the form will be reported at each time point using the full analysis population. The following variables will be summarised in accordance with section 9:

- Number of patients receiving the following treatment since the last evaluation:
  - a) Predniso(lo)ne
  - b) Rituximab
  - c) Azathioprine
  - d) Methotrexate
  - e) Mycophenolate Mofetil
  - f) Pneumocystis prophylaxis
    - i) Co-trimoxazole

---

 Rituximab treatments as recorded in the Follow-Up Form. Includes rituximab received as part of protocol and outside of protocol.

- ii) Dapsone
- iii) Other
- g) Aspirin
- h) Warfarin
- Doses of the following treatments at each visit:
  - a) Predniso(lo)ne (mg/day)
  - b) Azathioprine (mg/day)
  - c) Methotrexate (mg/week)
  - d) Mycophenolate Mofetil (g/day)
- In addition, the following derived variables (details in section 9.2) will be calculated across the maintenance phase (from month 4 to month 24) and overall (from randomisation to the end of the trial):
  - a) Average predniso(lo)ne dose (mg/day)
  - b) AUC of predniso(lo)ne dose (mg/day)
  - c) Azathioprine (mg/day)
  - d) Methotrexate (mg/week)
  - e) Mycophenolate Mofetil (g/day)

IV methylpredniso(lo)ne treatment, as recorded in the Treatment Form, will be reported at each time point using the full analysis population. The following variables will be summarised in accordance with section 9:

- IV methylpredniso(lo)ne treatment (Yes/No)
- Dose (mg)
- Cumulative IV methylpredniso(lo)ne dose (mg) up to 24 months
- Total IV methylpredniso(lo)ne dose in maintenance phase (mg) – derived variable, details in section 9.2

Reasons given for significant deviations from the GC protocol (defined as a  $\pm$  25% of the protocol specified dose, for period greater than 2 weeks) will be listed per patient, per visit in the appendix. Additionally a frequency table of the number of predniso(lo)ne deviations per patient per visit will be provided.

A count of the number of patients whose dose of azathioprine, methotrexate, or mycophenolate was changed will be reported per visit, and overall. Details (date of dose change, clinical side effects/intolerances, laboratory abnormalities, other

reasons) as recorded in Section 2 of the form will be listed per patient per visit in the appendix.

## 10 Efficacy Analyses

Efficacy analyses will be performed on the full analysis population. Additionally the primary efficacy analysis will be presented for the two per-protocol populations (maintenance and follow-up compliant populations).

### 10.1 Primary efficacy analysis

The primary efficacy outcome measure of the trial is relapse-free survival, where a relapse is either major or minor (see definitions above). **The primary analysis will be a Cox regression model adjusted for the stratification factors (ANCA type, relapse severity and prednisone induction regimen) for the difference in the distribution of relapse-free survival between the rituximab arm and the azathioprine (control) arm (two-sided at  $\alpha$ -level of 5%).** Assuming a proportional hazard holds, the hazard ratio together with the 95% confidence interval will be estimated using a Cox regression model adjusted for the stratification factors.

There will be a closed testing procedure, first the null hypothesis will be tested for a hazard ratio of 1 at all time points. If this is rejected at a 5% level then two further sub-hypothesis will be examined using time-varying covariates:

1. A hazard ratio of 1 up to 20 months post-randomisation (i.e. during treatment).
2. A hazard ratio of 1 after 20 months post-randomisation (i.e. post-treatment).

Kaplan-Meier estimates for relapse-free survival at 24 and 48 months and median relapse-free survival with the corresponding 95% confidence intervals by treatment allocation will be presented.

Additional analyses will consider in turn the interaction of treatment with each of the three stratification variables, i.e. ANCA type, relapse severity and induction regimen. Frequency tables and Kaplan-Meier plots, as well hazard ratios and 95%

---

 Time measured from enrolment, in reality this corresponds to 20 months and 44 months post-randomisation.

confidence intervals of a Cox proportional hazard model including interactions will be presented. These results are to be taken as exploratory only, as these analyses were not planned in the protocol, are likely under-powered and are not adjusted for multiple comparisons.

The following tables and figures will be reported, taking into account events occurring after randomisation (i.e. excluding the induction phase):

- No. of relapses:
  - a) by type (major or minor)
  - b) by phase (during treatment or post-treatment)
  - c) per participant
- No. of participants with a relapse (major or minor) by type at:
  - a) All time points
  - b) During treatment (up to month 20 post-randomisation)
  - c) Post-treatment (after 20 months post-randomisation)
- Kaplan–Meier curve with at risk population, from randomisation
  - i) Overall curve
  - ii) Stratified by ANCA type, relapse severity and induction regimen
- Median relapse-free survival (95% confidence interval)
- 24-month and 48-month relapse-free survival rate
- Hazard ratios at:
  - a) All time points
  - b) During treatment (up to month 20 post-randomisation)
  - c) Post-treatment (after 20 months post-randomisation).

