#### 5.2.1 Primary endpoint

The primary endpoint is the time to disease relapse (either minor or major relapse) from randomisation. Any patients who have not relapsed at study close will be censored. Further details of how relapse/censoring dates will be defined are given below (Table 1).

In the efficacy analysis, the date of the month 4 visit will be used as time-zero (i.e. randomisation). According to the protocol, patients might be randomised in advance of the month 4 visit (provided they achieved disease remission by the month 3 visit), however maintenance therapy (with either treatment) was not allowed to be administered before the month 4 visit.

---

 For a more in-depth description of randomisation procedures and trial's timelines, including definitions of the induction and maintenance phase, see Induction Phase SAP, section 9.1.1, and refer to the protocol, section 10.4.

Treatment duration is taken to be strictly 20 months post-randomisation, i.e. date of the month 4 visit + 20 months, and not the actual time of the month 24 visit when the last visit was administered. This affords a common timeline for all patients, irrespective of time slippages in the schedule of visits.

In the analysis, the censoring rules detailed in Table 1 will be implemented. Censoring time will be taken from the last assessment with no documented relapse (scheduled visit), the date of death (unscheduled visit) or the common close date. The time of relapse will be taken from the relapse form (unscheduled visit). Further particulars are detailed in section 10.3.

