**Table 1: Censoring rules**

Situation	Date of Relapse or Censoring	Outcome
No baseline assessments	Randomization	Censored
Relapse documented between scheduled visits	Unscheduled visit date	Relapsed
Drop-out with no relapse	Date of last assessment with no documented relapse	Censored
Treatment discontinuation for undocumented relapse	Date of last assessment with no documented relapse	Censored
Treatment discontinuation for toxicity or other reason, or protocol deviation	The patient will be followed up as per protocol and date of relapse or censoring observed accordingly	Relapsed/censored
Death due to relapse	Date of Death	Relapsed
Death due to other causes	Date of Death	Censored
Death or progression after more than one missed visit	Date of last assessment with no documented relapse	Censored

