Events happening between 6 and 12 months of the censoring date require further investigation. Depending on the last visit before any missing gaps, these events could fall after either one or two missed visits (e.g. an event 200 days after month 30 would happen after one missed visits, while an event 200 days after month 24

would happen after two missed visits). Thus the 12 months threshold is not strong enough to determine the outcome. The analysis code explicitly checks for such instances, which must then be adjudicated independently. None were found.

Likewise, by inspection, all deaths were by other causes and occurred before more than one missed visit, and thus no special considerations are needed (all patients who died were censored at the time of death).

An independent adjudication committee (blinded to treatment) will review all relapses and deaths. This will ensure that “deaths due to relapse” are recorded in the trial database as a relapse (i.e. there exists a corresponding relapse form). The censoring date of “deaths due to other causes” will also be verified in cases with more than one missed visit.

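### The SAP's Kaplan-Meier relapse-free survival rates censor deaths from other causes, so they estimate net freedom from relapse and should be renamed and given a competing-risk companion

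*SAP*

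**What the plan says.** SAP 5.2.1 defines the endpoint without reference to death: "The primary endpoint is the time to disease relapse (either minor or major relapse) from randomisation". Protocol 9.6.1 defines it the same way. The censoring tables in Protocol 9.6.1, SAP 5.2.1 (Table 1) and SAP 10.3 count a death due to relapse as an event and have a separate row, "Death due to other causes", which is censored at the date of death.

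SAP 10.1 changes the name: "The primary efficacy outcome measure of the trial is relapse-free survival". It plans "Kaplan-Meier estimates for relapse-free survival at 24 and 48 months", together with medians. A footnote explains that these times run from enrolment and that "in reality this corresponds to 20 months and 44 months post-randomisation". Figures 21 to 24, 26 and 28 in SAP 13 carry the same label.

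SAP 10.3 reports that "by inspection, all deaths were by other causes and occurred before more than one missed visit" and that "all patients who died were censored at the time of death". It gives no number of deaths. Neither document plans a cumulative incidence estimate or an analysis that counts non-relapse death as an event. Deaths are tabulated separately in SAP 11.4.

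**The concern.** Relapse-free survival ordinarily means alive and without relapse, so every death is an event. Here no non-relapse death is one. A reader who takes the 24- and 48-month figures at their label will believe that more patients are alive and in remission than the data show.

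The curve is not a direct estimate of observed relapse risk either. Kaplan-Meier with deaths censored estimates relapse as if death from other causes did not occur, provided such censoring is independent of relapse risk. When death competes, that curve lies above true relapse-free survival and below 1 minus the cumulative incidence of relapse. At stake are the absolute rates that will be quoted by arm, not the test of treatment effect.

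**Working it through.** **The plan's own figure.** Inputs from SAP 7: hazard ratio 0.42, 90% power, 5% level, 58 relapses; two-sided from SAP 10.1. Schoenfeld's formula for 1:1 allocation gives 4 × (1.960 + 1.282)² / (ln 0.42)² = 56 events, and 58 events give 91.0% power. The planned 4-year relapse-free rates agree with the hazard ratio: ln 0.75 / ln 0.50 = 0.415. The target counts relapses only, so censoring other-cause deaths is consistent with it.

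**Inputs for the rates.** Relapse-free rates of 75% (rituximab) and 50% (azathioprine) at 4 years come from SAP 7 and are treated here as running from randomisation. Assumptions: constant hazards; non-relapse death independent of relapse and equal in both arms; 4-year non-relapse mortality D of 2% to 10%. This range corresponds to roughly 2.5 to 13 deaths before relapse among 160 patients.

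**Formulas.** With λr the relapse hazard, λd = −ln(1 − D)/48, and t in months from randomisation:

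- Kaplan-Meier with deaths censored targets exp(−λr t).
- Alive and relapse-free is exp(−(λr + λd) t).
- Cumulative incidence of relapse is λr/(λr + λd) × [1 − exp(−(λr + λd) t)].

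**Example, D = 5%, t = 44.** λd = 0.001069.

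- Rituximab, λr = 0.005993: Kaplan-Meier 0.768; alive and relapse-free 0.733; cumulative incidence 0.8487 × 0.2671 = 0.227. Since 1 − 0.768 = 0.232, relapse risk is overstated by about 0.5 points.
- Azathioprine, λr = 0.014441: Kaplan-Meier 0.530; alive and relapse-free 0.505; cumulative incidence 0.9311 × 0.4946 = 0.4605. Since 1 − 0.5297 = 0.4703, relapse risk is overstated by about 1 point.

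**At 44 months post-randomisation (the 48-month rate):**

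| Arm | D | Kaplan-Meier | Alive and relapse-free | Gap (points) | 1 − cumulative incidence |
|---|---|---|---|---|---|
| Rituximab | 2% | 76.8% | 75.4% | 1.4 | 77.0% |
| Rituximab | 5% | 76.8% | 73.3% | 3.5 | 77.3% |
| Rituximab | 10% | 76.8% | 69.7% | 7.1 | 77.9% |
| Azathioprine | 2% | 53.0% | 52.0% | 1.0 | 53.4% |
| Azathioprine | 5% | 53.0% | 50.5% | 2.4 | 53.9% |
| Azathioprine | 10% | 53.0% | 48.1% | 4.9 | 54.9% |

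**At 20 months (the 24-month rate)** the alive-and-relapse-free figure falls from 88.7% to between 88.0% and 84.9% on rituximab, and from 74.9% to between 74.3% and 71.7% on azathioprine. The gap is 0.6 to 3.8 points.

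**Per death, without assuming a mortality rate.** With 80 patients per arm and no administrative censoring, one death before relapse separates the two curves at 44 months by between S(44)/80 and 1/80, where S is the Kaplan-Meier value. That is 0.96 to 1.25 points on rituximab (0.768/80 to 1/80) and 0.66 to 1.25 on azathioprine (0.530/80 to 1/80).

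**Simulation check.** In 2,000 trials with 80 patients per arm, censoring spread over 32 to 44 months and D = 5%, the mean gap at 40 months was 3.3 points (rituximab) and 2.3 points (azathioprine). The death-censored curve was at or above the relapse-or-death curve in every run.

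**The case against.** The estimand is not hidden. Both documents define the endpoint as time to relapse, and the censoring of other-cause deaths is stated in every censoring table. Protocol 7.3.1 uses the same survival label for the pilot cohort and then gives percentages relapsed, so the term serves as shorthand for freedom from relapse. Against the endpoint the protocol chose, Kaplan-Meier is a consistent net estimate if censoring is independent. This stands, and it confines the problem to the label and the interpretation of the absolute rates.

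A reader might infer that dead patients are being counted as in remission. They are not: censoring removes them from the risk set and in effect gives them the later relapse experience of those still followed. A reader might also infer that the 24- and 48-month rates are the only planned figures near the secondary endpoint on maintained remission. SAP 9.7 summarises disease status, including remission, at every visit, and SAP 10.1 counts participants with a relapse. However, the visit summaries use non-missing denominators (SAP 8.5 and 9), so patients who have died drop out of them and they do not repair the gap.

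Deaths are visible through SAP 11.4 and the CONSORT diagram, though nowhere combined with relapse. Precision is also limited. With 80 per arm the 95% interval at 44 months is at best about ±9 points (1.96 × √(0.768 × 0.232/80)) on rituximab and ±11 points (1.96 × √(0.530 × 0.470/80)) on azathioprine. Every shift shown is smaller. That limits the practical weight but does not remove a shift whose direction is known.

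**Conclusion.** The point holds as a minor one about labelling and absolute rates. Read as relapse-free survival, the planned rates are too high whenever a patient dies before relapse within the horizon. SAP 10.3 indicates that this happened, since it describes deaths censored at the time of death. The size, about 1 to 7 points at 44 months, rests on assumed 4-year mortality of 2% to 10%, equal in both arms, and constant hazards. With few deaths it is 1 to 2 points. Read as relapse risk, 1 minus Kaplan-Meier errs by less: at 5% mortality, about 0.5 points on rituximab and about 1 point on azathioprine.

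Two stronger readings are not supported. The first is that the rates are simply too high. That is true only against the composite the label names; against cumulative relapse, Kaplan-Meier freedom from relapse is slightly too low. The second is that the primary result is biased. The Cox model estimates a valid cause-specific relapse hazard ratio, and the closed test and the 58-relapse target concern relapses only. Making death an event would answer a different question: under equal mortality the planned ratio of 0.415 would move to about 0.43 (2%) or 0.49 (10%).

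**What to change.** - Keep the Cox analysis and the closed test as they are.
- In SAP 10.1 and the figure titles in SAP 13, replace the survival label with time to relapse (medians) and freedom from relapse (rates and curves). Do the same for the secondary outcomes in SAP 10.2, which mirror the primary analysis.
- Report the cumulative incidence of relapse by arm at 20 and 44 months post-randomisation, with non-relapse death as a competing event (Aalen-Johansen), and give the number of such deaths by arm beside it.
- If the term relapse-free survival is kept anywhere, attach it to one supportive estimate in which relapse or any death is the event.
- Reconcile the rule in SAP 10.3 that takes the latest of last completed visit, other-cause death and common close with the later statement that patients who died were censored at death. Read literally, the rule could carry some dead patients forward to common close.

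The cost is SAP wording and one extra table or figure. No new data are needed, and the sample size and primary test do not change.
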